7.3.3. DF/HCC Adverse Event Reporting Guidelines

Investigative sites within DF/HCC will report AEs directly to the DFCI Office for Human Research Studies (OHRS) per the DFCI IRB reporting policy.

7.3.4. Protocol-Specific Adverse Event Reporting Exclusions

For this protocol only, the AEs/grades listed below do not require expedited reporting to the Overall PI or the DFCI IRB. However, they still must be reported through the routine reporting mechanism (i.e. case report form).

Events not considered to be serious adverse events for this protocol are:
-Hospitalization for seizure
-Emergency outpatient treatment for an event not fulfilling the serious criteria outlined above and not resulting in inpatient admission

7.4. Reporting to Hospital Risk Management

Participating investigators will report to their local Risk Management office any participant safety reports, sentinel events or unanticipated problems that require reporting per institutional policy.

7.5. Routine Adverse Event Reporting

All Adverse Events **must** be reported in routine study data submissions to the Overall PI on the toxicity case report forms. **AEs reported through expedited processes (e.g., reported to the IRB, FDA, etc.) must also be reported in routine study data submissions.**

8. PHARMACEUTICAL INFORMATION

A list of the adverse events and potential risks associated with the agent administered in this study can be found in Section 7.1.

8.1. Perampanel

8.1.1. Description

The chemical name of the active ingredient is 2-(1',6'-dihydro-6'-oxo-1'-phenyl[2,3'-bipyridin]-5'-yl)-benzotrile, hydrate (4:3). The molecular formula is C₂₃H₁₅N₃O • 3/4H₂O and the molecular weight is 362.90 (349.39 for anhydrous perampanel).

Perampanel is rapidly and completely absorbed after oral administration with negligible first-pass metabolism. Median time to reach peak concentration (t_{max}) ranged from 0.5 to 2.5 hours under fasted condition. Co-administration of perampanel tablet with a high fat meal had no impact on the total exposure (AUC_{0-inf}) of perampanel and reduced the peak plasma concentration (C_{max}) of perampanel by 11%-40%. The t_{max} was delayed by approximately 1-3 hours in fed state compared to that under fasted conditions.

Data from in vitro studies indicate that, in the concentration range of 20 to 2000 ng/mL, perampanel is approximately 95- 96% bound to plasma proteins, mainly bound to albumin and α 1-acid glycoprotein. Blood to plasma ratio of perampanel is 0.55-0.59.

Perampanel is extensively metabolized via primary oxidation and sequential glucuronidation. Oxidative metabolism is primarily mediated by CYP3A4/5 and to a lesser extent by CYP1A2 and CYP2B6, based on results of in vitro studies using recombinant human CYPs and human liver microsomes. Other CYP enzymes may also

be involved.

Following administration of radiolabeled perampanel, unchanged perampanel accounted for 74-80% of total radioactivity in systemic circulation, whereas only trace amounts of individual perampanel metabolites were detected in plasma.

Following administration of a radiolabeled perampanel tablet dose to 8 healthy elderly subjects, 22% of administered radioactivity was recovered in the urine and 48% in the feces. In urine and feces, recovered radioactivity was primarily composed of a mixture of oxidative and conjugated metabolites. Population pharmacokinetic analysis of pooled data from 19 Phase 1 studies reported that $t_{1/2}$ of perampanel was 105 hours on average. Apparent clearance of perampanel in healthy subjects and patients was approximately 12 mL/min.

The concomitant use of known moderate and strong CYP3A4 inducers including carbamazepine, phenytoin, or oxcarbazepine with FYCOMPA decreased the plasma levels of perampanel by approximately 50-67%.

Perampanel C_{max} and AUC_{0-72h} were not altered when a single 6-mg dose of perampanel tablet was administered to healthy female subjects following a 21-day course of oral contraceptives containing ethinylestradiol 30 µg and levonorgestrel 150 µg. Co-administration of perampanel 4 mg tablet once daily with an oral contraceptive containing ethinylestradiol 30 µg and levonorgestrel 150 µg for 21 days did not alter C_{max} or AUC_{0-24h} of either ethinylestradiol or levonorgestrel in healthy female subjects. In another study, a single dose of the oral contraceptive was administered following 21-day once daily dosing of perampanel 12 mg or 8 mg tablets in healthy females. Perampanel at 12 mg did not alter AUC_{0-24h} of ethinylestradiol but decreased its C_{max} by 18%, and also decreased C_{max} and AUC_{0-24h} of levonorgestrel by 42% and 40%, respectively. Perampanel at 8 mg did not have significant effect on C_{max} or AUC_{0-24h} of either ethinylestradiol or levonorgestrel, with a decrease in AUC_{0-24h} of levonorgestrel (9% on average).

8.1.2. Form

Perampanel drug product will be as follows:

- 4mg tablet, red, round, debossed with “4” on one side and “C 277” on the other
- 6mg tablet, pink, round, debossed with “6” on one side and “C 294” on the other
- 8mg tablet, purple, round, debossed with “8” on one side and “C 295” on the other

Tablets contain the following inactive ingredients: lactose monohydrate, low substituted hydroxypropyl cellulose, povidone, microcrystalline cellulose, magnesium stearate, hypromellose, polyethylene glycol, talc, titanium dioxide, red ferric oxide (4mg, 6mg, 8mg), black ferric oxide (8mg).

8.1.3. Storage and Stability

Tablets: store at 20°C to 25°C (68°F to 77°F); excursions permitted to 15°C to 30°C (59°F to 86°F).

8.1.4. **Compatibility**

There are no known compatibility issues.

8.1.5. **Handling**

Routine handling is recommended.

8.1.6. **Availability**

Perampanel is commercially available and manufactured by Eisai Inc; it will be provided free of charge for this study by Eisai.

8.1.7. **Preparation**

No preparation is required.

8.1.8. **Administration**

Perampanel will be administered by mouth once a day.

8.1.9. **Ordering**

Investigators will order and acquire perampanel directly from Eisai Inc.

8.1.10. **Accountability**

The investigator, or a responsible party designated by the investigator, will maintain a careful record of the inventory and disposition of the agent using the NCI Drug Accountability Record Form (DARF) or another comparable drug accountability form. (See the NCI Investigator's Handbook for Procedures for Drug Accountability and Storage.)

8.1.11. **Destruction and Return**

Perampanel will be destroyed on site or returned to the research pharmacy according to institutional policies, and documented in the Drug Accountability Record Form.

9. **BIOMARKER, CORRELATIVE, AND SPECIAL STUDIES**

9.1. Electrocorticography

As the primary outcome for this study, HFOs will be measured in intra-operative ECoG recordings from all participants in Cohort 1 and Cohort 2. ECoG data will be analyzed post-operatively. HFOs will be visually identified after filtering (FIR, order 500, bandpass 80-500 Hz) using Persyst Insight (Persyst Development Corp, Solana Beach, CA). The rate of HFOs per channel per subject will be measured for analysis.

ECoG is a standard clinical procedure utilized for epilepsy and brain tumor surgery. There will be no deviations from standard institutional protocols for this study. The investigators are experienced in the performance of this procedure and analysis of ECoG data. The use of ECoG is expected to increase the length of surgery by 15-20 minutes.

There is a low chance (3-4%) that ECoG may reveal subclinical electrographic seizures or highly epileptiform activity that would not be otherwise identified,³¹ and would allow for immediate treatment to decrease the risk of intra-operative brain injury.

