1. OBJECTIVES

Study Hypothesis #1: Perampanel treatment reduces peritumoral hyperexcitability in newly diagnosed high grade glioma (HGG).

Study Hypothesis #2: Perampanel treatment in newly diagnosed HGG is associated with improvement in seizure control.

1 Study Design

This pilot study (Cohort 1) in participants with newly discovered radiologic lesions consistent with HGG evaluates the effect of perampanel on peritumoral hyperexcitability, measured by the rate of high frequency oscillations on intra-operative electrocorticography (ECoG), compared to a contemporary observational control group (Cohort 2) of participants undergoing ECoG and standard peri-operative seizure management. To estimate the effect size of early perampanel treatment on ongoing seizure control, participants in Cohort 1 will be maintained post-operatively on perampanel, adjusted on a clinical basis until evidence of disease progression (or maximum of 12 months), and compared to participants in Cohort 2 receiving standard of care post-operative seizure management.

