4 REGISTRATION PROCEDURES

In order to maximize enrollment into the pilot study over a short time, and given the difficulty in recruiting participants within a narrow pre-operative time window, we will perform concurrent recruitment into the single arm pilot group (Cohort 1) and a contemporary observational control group (Cohort 2). Eligible participants will be informed and provided the consent forms for both study groups, and those who have no preference will be enrolled in the cohort with the smaller current enrollment, while those who express a preference will be enrolled into the cohort of their preference (up to a maximum enrollment of 10 per cohort). This will enable eligible participants to be enrolled who decline to be randomized. We do not anticipate a systemic bias in endpoints using this method of enrollment, as potentially confounding factors (described in Section 13) are not expected to influence enrollment preferences, although we cannot completely exclude it.

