5. TREATMENT PLAN

5.1. Treatment Regimen

Perampanel will be given every day until meeting the study endpoint(s). Reported adverse events and potential risks are described in Section 7. Appropriate dose modifications are described in Section 6. Other anti-seizure medication(s) may be administered during perampanel maintenance therapy as clinically indicated.

Cohort 1

Participants who are already receiving an anti-seizure medication pre-operatively for treatment of tumor-associated seizures will receive their last dose at least 36 hours before scheduled surgery start-time, and then will be switched to perampanel. The loading dose of perampanel will be 6mg by mouth, given on the day prior to surgery (12-36 hours before scheduled start time), followed by a maintenance dose of 4mg by mouth once a day. Participants will be requested to maintain a drug diary of each dose of medication. The drug diary will be returned to clinic staff at the end of each month.

Study day	Perampanel dose
Day 1 (load)	6mg
Day 2+ (maintenance)	4mg

Cohort 2

Perioperative and post-operative seizure management will be performed by the primary treating physician(s) according to institutional standards.

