5.3.3. Other Modality(ies) or Procedures

Electrocorticography (ECoG):

Intraoperative electrocorticography (ECoG) will be performed for 10 minutes using an Xltek machine (Natus Medical Inc, Pleasanton, CA), sampled at 1000 Hz per channel, with a subdural 4x5 electrode grid overlying the tumor margins, according to institutional clinical protocols. At least 10 minutes prior to ECoG, inhaled anesthetics and propofol infusion will be stopped, as per standard institutional practices. Subsequent tumor resection will be performed at the discretion of the neurosurgeon, and high frequency activity will be analyzed independently post-operatively (see Section 9.1).

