13.1. Study Design/Endpoints

Pilot Study: Preliminary Study

- Primary objective: Compare rates of peritumoral HFOs (mean number of HFOs per minute) between participants treated with perampanel versus standard of care.
- Secondary objective: Compare time to seizure recurrence between participants treated with perampanel versus standard of care up to the time of HGG progression.
- Maximum total accrual: 10 participants in Cohort 1, 10 participants in Cohort 2.
- Sample size justification: Using the mean HFO rate across participants receiving standard of care (Cohort 2) as the normalized ineffective rate ($P_1=1.0$), we define a target effective rate for the treatment arm (Cohort 1) of $P_2=0.60$. Using a two sample power calculation, the intended sample size of 10 participants in each cohort will provide 82.5% power to detect a true 40% or greater reduction in the normalized mean HFO rate with perampanel compared to standard of care ($\alpha=0.05$, two-sided).
- Statistical methods for primary objective: The primary endpoint is the mean number of HFOs per minute. This will be averaged across participants in each cohort, and compared using the Mann-Whitney U test (two-sided, $\alpha=0.05$). In sensitivity analyses, we will compare HFO rates between cohorts stratified by potential confounding variables, including temporal lobe tumor location, IDH1/2 mutation, and pre-operative seizures.
- Statistical methods for secondary objective: The secondary endpoint is the time to first post-operative seizure. Time to first post-operative seizure will be estimated in time-to-event analysis from the date of surgery using the Kaplan-Meier method. Comparison

between Cohort 1 and Cohort 2 will be performed using the log-rank test ($\alpha=0.05$). In sensitivity analyses, we will compare time to first post-operative seizure between cohorts stratified by potential confounding variables, including temporal lobe tumor location, extent of resection (gross total vs subtotal resection), presence of IDH1/2 mutation, and presence of pre-operative seizures.

- Data processing and statistical analysis will be performed using R 3.5.3 (The R Foundation for Statistical Computing).
- These results will be used to support or refute the hypothesis that perampanel has targeted anti-epileptogenic activity in glioma-associated epilepsy, and may inform the design and feasibility of future clinical studies of targeting the glutamatergic pathway in this patient population.

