Correlative Analysis: Intraoperative Stereotactic Molecular Imaging

- Aim 1: Correlate lactate/pyruvate ratio by mass spectrometry with HFO rate in adjacent ECoG electrodes.
- Aim 2: Correlate glutamate and GABA signal intensities by mass spectrometry imaging with HFO rate in adjacent ECoG electrodes.
- Aim 3: Correlate anti-seizure drug signal intensity by mass spectrometry imaging with HFO rate in adjacent ECoG electrodes.
- Statistical analysis: correlations will be measured using Spearman's rank correlation coefficient.

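### The primary endpoint is counted by eye from the ECoG traces, and nothing in the plan masks the reader to cohort

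*Combined protocol and SAP*

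**What the plan says.** Section 9.1 makes HFOs on ECoG the primary outcome in both cohorts, analysed after surgery, and states that "HFOs will be visually identified after filtering (FIR, order 500, bandpass 80-500 Hz) using Persyst Insight". Section 13.1 turns the count into mean HFOs per minute and compares the cohorts with a two-sided Mann-Whitney test at 0.05, with at most 10 participants in each.

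Treatment is open. Section 1 describes Cohort 1 as "compared to a contemporary observational control group (Cohort 2) of participants undergoing ECoG and standard peri-operative seizure management", and Section 5.1 says of Cohort 2 that "Perioperative and post-operative seizure management will be performed by the primary treating physician(s) according to institutional standards". There is no placebo. Under Section 4, participants without a preference join the smaller cohort, and "those who express a preference will be enrolled into the cohort of their preference".

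On who reads and under what conditions, there are two statements. Section 5.3.3 says "Subsequent tumor resection will be performed at the discretion of the neurosurgeon, and high frequency activity will be analyzed independently post-operatively" and points to Section 9.1. Section 9.1 adds "The investigators are experienced in the performance of this procedure and analysis of ECoG data". Neither mentions cohort, coding of the recordings or masking.

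**The concern.** A count made by eye on filtered traces depends on where the reader sets the threshold for an event. A reader who knows that a trace comes from a perampanel patient, and knows the hypothesis, may mark differently without intending to. The treatment cannot be hidden from participants or treating staff in this design, so masking the reader is the only protection available for the measurement itself.

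The stakes are high because Section 13 describes the protocol as powered for this outcome, and Section 13.1 says the results will support or refute the mechanistic hypothesis. Nor could the planned analyses repair the damage. In the sensitivity analyses, "we will compare HFO rates between cohorts stratified by potential confounding variables, including temporal lobe tumor location", together with IDH1/2 mutation and pre-operative seizures. None of these concerns the reading. The same HFO rates also feed the exploratory aims, for example "Correlate anti-seizure drug signal intensity by mass spectrometry imaging with HFO rate in adjacent ECoG electrodes", so a biased count would carry over to them.

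**Working it through.** **Is the reader masked anywhere?** Placing the relevant statements side by side:

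- Section 9.1 gives the filter, the software and visual identification. It specifies no automated detector, event-marking rule, named reader or masking.
- Section 5.3.3 uses the word independently, but the contrast in that sentence is with the neurosurgeon's resection decision. Its most natural meaning is that the reading does not guide the resection. It does not say that cohort is withheld.
- The remark about experienced investigators suggests, without proving, that the study team reads the traces.
- Sections 1.1 and 5.3.3 fix the frequency band, the 10-minute recording, the tumour margin, the 4x5 grid, the sampling rate and the anaesthetic stop. These standardise the recording. They do not fix what the reader accepts as an event.

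So the plan as written permits the count to be made with cohort known.

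**What variability does the plan imply?** Section 13.1 states 82.5% power for a normalised mean of 0.60 against 1.0 with n = 10 per cohort and two-sided α = 0.05. It gives no standard deviation, so the figure cannot be reproduced directly. Solving backwards by the normal formula:

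SD = 0.40 / [(z₀.₉₇₅ + z₀.₈₂₅) × √(2/10)] = 0.40 / [(1.960 + 0.935) × 0.447] = 0.309.

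The noncentral t version gives 0.292. If the calculation was a two-sample comparison of means, the plan therefore assumes a coefficient of variation (CV) of about 0.29 to 0.31.

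**What would a reader bias do?** The documents give no figure for reader error, so every bias size below is an assumption. Suppose perampanel has no effect and the reader under-counts Cohort 1 by a fraction b.

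Share of the target effect mimicked = b / 0.40:

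- b = 0.10: 25%
- b = 0.20: 50%
- b = 0.30: 75%

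False-positive rate of the planned test, by simulation:

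- HFO rates are lognormal with equal means, 10 per cohort, and Cohort 1 is multiplied by (1 − b).
- The exact two-sided Mann-Whitney test rejects at U ≤ 23 or U ≥ 77, which has exact size 4.3%.
- Each cell has 200,000 runs.

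| Assumed CV | b = 0 | b = 0.10 | b = 0.20 | b = 0.30 |
|---|---|---|---|---|
| 0.29 | 4.4% | 11% | 34% | 70% |
| 0.5 | 4.4% | 7% | 15% | 32% |
| 1.0 | 4.3% | 5% | 8% | 13% |
| 1.5 | 4.3% | 5% | 6% | 9% |

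With normal data at SD 0.292, the Mann-Whitney rates for b = 0.10, 0.20 and 0.30 are 10%, 27% and 55%. The pattern does not depend on the lognormal shape.

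The lower rows need a caution. In the same simulation, power for a true 40% reduction is about 58% at CV 0.5, 22% at CV 1.0 and 15% at CV 1.5. A 10% under-count barely moves the test only where the trial has little power in any case. If variability is as low as the power statement needs, the test is most exposed.

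**The case against.** **The word independently may mean more than it appears to.** It could refer to independence from the surgical team, and reading procedures may sit in institutional ECoG protocols that are not part of the plan. This stands as a limit: the point concerns what is written, and the reader may be masked in practice. It does not show that cohort is withheld. If masking is intended, it needs only to be stated.

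**Lack of randomisation and lack of placebo are declared choices in a pilot.** This is fair. Section 4 explains the enrolment method and admits that bias from it cannot be completely excluded. These features matter here only because they leave treatment open. Reading bias is a separate problem and, unlike enrolment bias, can be prevented cheaply.

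**The magnitude is invented.** The bias sizes and CVs are indeed assumptions, and the share of target is simple division. The table shows how sensitive the test would be. It is not evidence that any bias exists. Anchoring it to the variability implied by the plan's own power strengthens the illustration.

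**A marking rule and masking are different gaps.** This is also true: a masked reader can lack a rule, and a reader with a rule can be unmasked. They belong together in the remedy because masking prevents differential marking while the rule limits drift.

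**Conclusion.** The concern holds. The primary endpoint is a visual count compared between openly treated, non-randomised cohorts. The available text does not mask the reader, and no stated analysis would correct a reading bias once it had entered the counts.

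Whether such a bias would occur, and in which direction, is unknown. Under the assumptions above, a 20% under-count in Cohort 1 with no drug effect would raise the false-positive rate from 4.3% to between about 6% (CV 1.5) and 34% (CV 0.29).

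This is a change the sponsor should make, with medium confidence, since the claim rests on absence from the documents.

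**What to change.** Add to Section 9.1:

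1. A named team member who does not read traces exports each recording under a random code and holds the key. Office of Data Quality staff could do this if that office agrees; Section 12.1.1 gives it data management and quality checks but does not mention ECoG files. Cohort, date, anti-seizure medication and seizure history are removed. Electrode positions and technical notes are kept, because the reading and the correlative aims in Section 13.1 need them. Anaesthetic timing is given as minutes from the start of recording.
2. One written HFO event definition is fixed before any recording is read.
3. The reader, identified by role, marks all recordings in random order, masked to cohort, using that definition. The plan states whether any reader was present at surgery.
4. Counts are locked before the code is linked to cohort.

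The cost is the coding of at most 20 files already due for post-operative analysis, a short definition and a locked table. Sample size, treatment and participant procedures do not change. The opening page lists coordinator, research nurse and data manager as not applicable, so the key-holder has to be named.

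The downsides are that reading waits for batching, a reader who was in theatre may recognise some cases, and the retained notes must be checked for clues to cohort. Confounding from preference-based enrolment remains and should still be acknowledged when results are reported.

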9.2. Laboratory Correlative Studies

9.2.1. Intraoperative Stereotactic Molecular Imaging

This protocol involves an optional ancillary/exploratory tissue study involving mass spectrometry analysis and histopathology evaluation. The aim of this correlative analysis is to measure the metabolic profile, neurotransmitter profile, and study drug tissue distribution in resected tissue specimens. Although glutamatergic excitotoxicity is thought to contribute to tissue necrosis,²⁶ the relationship between excitotoxic tissue injury and electrophysiologic biomarkers in human glioma is poorly understood. We hypothesize that peritumoral hyperexcitability and excitotoxic metabolic profiles will be correlated with the tissue distribution and concentration of anti-seizure medications in the peritumoral microenvironment. We propose to study the correlation between ECoG high frequency activity, histopathology, drug tissue distribution, neurotransmitter concentrations, and metabolic profile from surgical specimens.

This analysis of surgical tissue will be performed in collaboration with [name], using methods according to Partners IRB protocol 2011P002387. Identification of drug and metabolites in surgical tissue specimens will be performed with MALDI MSI and a neuronavigation system to allow the subsequent infusion of molecular information into the MRI. This technique has been validated by [name] and collaborators for detection of tumor metabolites,³² tumor subtype classification,³³ and therapeutic drug distribution.³⁴ Given that multiple samples will be analyzed per participant, this study enrolling up to 20 participants across cohorts will be sufficient to demonstrate interpretable and meaningful results.

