9.2.1.1. Collection of Specimens

No changes will be made to the routine clinical care of patients in this study. All aspects of the surgical management including preoperative and postoperative care will be carried out per the standard of care. Specimens will be collected for the study during tumor resection. The study

will not affect the manner or quantity of tissue removed. In addition to the bulk tumor specimen as routinely sent, numerous small specimens will be collected during the resection using tumor forceps at sampling positions registered to pre-operative MRI images using a navigation system (General Electric Instatrak or BrainLab Vector Vision). All specimens will be sent to the BWH Tissue Biorepository. When the Tissue Biorepository has confirmed that enough tissue has been collected to make a diagnosis, specimens will be made available MALDI MSI.

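### Minor, exploratory aims only: the plan gives a plain Spearman coefficient for several tissue-electrode pairs per participant, with no handling of participant, cohort or drug, so precision could be overstated and Aim 3 could repeat the cohort comparison

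*Combined protocol and SAP*

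**What the plan says.** Section 9.2.1 sets the status of this work: "This protocol involves an optional ancillary/exploratory tissue study involving mass spectrometry analysis and histopathology evaluation". Its sample size argument is "Given that multiple samples will be analyzed per participant, this study enrolling up to 20 participants across cohorts will be sufficient"; the sentence ends by claiming interpretable, meaningful results and gives no calculation.

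The data are repeated within participant. Section 9.2.1.1 says "numerous small specimens will be collected during the resection using tumor forceps at sampling positions registered to pre-operative MRI images". Section 5.3.3 records ECoG "with a subdural 4x5 electrode grid overlying the tumor margins", and Section 9.1 measures the HFO rate by channel.

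Section 13.1 lists three aims, each pairing a tissue measure with the HFO rate in nearby electrodes. Aim 3 reads "Correlate anti-seizure drug signal intensity by mass spectrometry imaging with HFO rate in adjacent ECoG electrodes" and names no drug, whereas Section 9.2.1.2 measures both perampanel and levetiracetam. The whole analysis statement is "correlations will be measured using Spearman's rank correlation coefficient".

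No other section adds a unit of analysis or a rule for participant, cohort or drug. Sections 13.5 and 13.6 refer back to 13.1, and the stratified sensitivity analyses in 13.1 concern the primary and secondary endpoints only.

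**The concern.** There are two separate issues.

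**Clustering.** The natural data row is a tissue-electrode pair, with several rows per person. Section 9.2.1 lets the number of samples make up for the small number of people and counts both cohorts together. An analyst who follows the text literally could put all pairs into one Spearman coefficient. If both variables differ between people, the ordinary p-value or interval then treats, say, 100 pairs from 20 people as 100 independent observations.

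**Cohort mixing in Aim 3.** Cohort 1 takes perampanel before surgery. Under Section 5.1, those already on another anti-seizure drug "will receive their last dose at least 36 hours before scheduled surgery start-time, and then will be switched to perampanel". Cohort 2 has institutional standard management. With cohorts combined, perampanel signal is close to an indicator of Cohort 1. A cohort difference in HFO rate, which is the primary hypothesis, then appears as a drug-HFO correlation even if local concentration has no relation to local HFO rate.

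What is at stake is how exploratory results are read, not any trial decision.

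**Working it through.** The documents give no power, precision, alpha, pair count or ICC for these aims, so there is no figure to reproduce. What follows is illustrative.

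**Inputs.** From the plan: at most 10 + 10 = 20 participants (Section 13.1). Assumed: m = 3, 5 or 10 pairs each, a range of ICCs, a nominal two-sided 5% test, normal variables with a participant effect, and no true association.

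**Step 1: pooled Spearman.** The variance inflation is approximately D = 1 + (m − 1) × ICC(x) × ICC(y). Because the ICCs multiply, D = 1 whenever either is zero. The approximate false-positive rate is P(|Z| > 1.96/√D). For 20 participants and m = 5 (100 pairs):

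| ICC x / y | D | Effective pairs, 100/D | Approximate rate | Simulated rate |
|---|---|---|---|---|
| 0.5 / 0 | 1.00 | 100 | 5.0% | about 5% |
| 0.2 / 0.2 | 1 + 4 × 0.04 = 1.16 | 86 | P(\|Z\| > 1.82) = 6.9% | 6-7% |
| 0.5 / 0.5 | 1 + 4 × 0.25 = 2.00 | 50 | P(\|Z\| > 1.39) = 17% | about 15% |
| 0.8 / 0.8 | 1 + 4 × 0.64 = 3.56 | 28 | P(\|Z\| > 1.04) = 30% | about 29% |

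Pair count matters too. At ICC 0.5 in both and 20 participants, the simulated rate is about 10% with m = 3 and 26% with m = 10.

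**Step 2: an analysis that respects participant.** Computing rho within each participant and putting a t interval on the mean gave 4.5-5.7% in all settings simulated. Spearman on participant means, for the between-participant relation, also stayed near 5%.

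**Step 3: precision of mean within-participant rho.** With no association, one participant's rho has variance 1/(m − 1). The 95% half-width is therefore about t(N − 1) / √(N(m − 1)).
- 20 participants, 5 pairs: 2.093/√80 = 0.23. Treating 100 pairs as independent would give 1.96/√99 = 0.20.
- 20 participants, 3 pairs: 2.093/√40 = 0.33.
- 10 participants, 5 pairs: 2.262/√40 = 0.36 (simulated 0.35).
- 10 participants, 10 pairs: 2.262/√90 = 0.24 (simulated 0.23).

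**Step 4: precision of the between-participant relation.** The critical value is r = t/√(t² + n − 2). For n = 20 it is 2.101/√(4.414 + 18) = 0.44, and for n = 10 it is 2.306/√(5.318 + 8) = 0.63.

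**Step 5: Aim 3 by reasoning.** Suppose perampanel signal is near zero in Cohort 2, positive in Cohort 1, and unrelated to HFO rate inside Cohort 1. If HFO rates are lower in Cohort 1, high signal goes with low HFO rate across the combined set, so rho is negative. That rho reflects cohort membership only. Within Cohort 1 alone the expected rho is zero. A within-participant rho also removes the problem, because cohort is constant within a participant.

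**The case against.** The strongest reply is that this is a missing detail in optional work. Section 13.1 says correlations are to be measured; it states no test, interval, alpha or decision. MRI-registered sampling positions and nearby electrodes suggest a local, within-participant analysis, and measuring the two drugs separately suggests analysing them separately. The ICCs are unknown, and at 0.1-0.2 the inflation with 5 pairs is only 5-7%. All of this stands and keeps the point minor. It does not remove the point, because the text permits the weaker analysis and nothing directs the analyst to the better one.

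A reader might infer several stronger things that the documents do not support:
- **That the plan pools and tests pairs.** It does not say so; Section 9.2.1 only makes that reading plausible.
- **That extra samples per participant add nothing, so the sufficiency sentence is wrong.** Step 3 shows otherwise: at 20 participants, moving from 3 to 5 pairs narrows the half-width from 0.33 to 0.23. What the sentence lacks is the other half, the number of participants.
- **That a combined Aim 3 correlation would be spurious.** If perampanel causes the cohort difference, the correlation is a real exposure effect. It repeats the primary comparison, however, and shows no local concentration relation.
- **That the chance of a significant combined Aim 3 result can be quoted for this trial.** The plan gives no HFO standard deviation. Back-solving one from the 82.5% power needs a t or normal formula that the plan does not state, and a normal model puts some HFO rates below zero. No such rate is offered here.

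**Conclusion.** The point holds as a minor one, confined to the optional exploratory aims. The named method does not match the repeated structure of the data. Overstated precision is conditional on pooling and on clustering in both variables. In the assumed case of 20 participants with 5 pairs each, a nominal 5% test then runs at about 6-7%, 15% and 29% for ICC 0.2, 0.5 and 0.8 in both, and at about 5% if either variable is unclustered.

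The Aim 3 issue is conditional on combining cohorts and is stated by direction only. It matters because the hypothesis, "We hypothesize that peritumoral hyperexcitability and excitotoxic metabolic profiles will be correlated with the tissue distribution and concentration of anti-seizure medications", covers both local distribution and overall concentration; these are different relations and one coefficient cannot separate them.

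This is an omission with a clear better method, not a demonstrated error.

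**What to change.** In the correlative analysis of Section 13.1, replace the plain coefficient with Spearman's rho computed within each participant and summarised across participants with a t interval. Report the between-participant relation separately, using participant means.

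For Aim 3, analyse each drug separately: perampanel within Cohort 1, and levetiracetam only in participants receiving it. Apply the same restriction to the participant-mean analysis, since means across combined cohorts would mix cohort and drug again.

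In Section 9.2.1, base the precision statement on both the number of participants who join the optional study and the number of pairs from each.

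A percentile bootstrap over participants should not be listed as an equal alternative. With these numbers it is somewhat liberal, at about 8-11% with 10 participants and 6-10% with 20 against a nominal 5%, and 10 is the ceiling for perampanel within Cohort 1.

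The cost is wording in two sections and slightly more analysis, with no new data. Intervals are wider: the half-width is about 0.23 with 20 participants and 5 pairs each, and 0.35 with 10 and 5. Since participation is optional and tissue is released only once diagnosis is secured (Section 9.2.1.1), Aim 3 may be imprecise, and the report should say so.
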